9.4.1 Planned Analyses

9.4.1.1 Interim Analysis and Early Stopping Guidelines

Safety data will be reviewed on an ongoing basis.

During dose exploration and formally during DLRMs, Amgen, in consultation with the site investigators, will review all available cumulative data by cohort prior to making dose escalation or dose de-escalation recommendations. Adverse events and DLTs observed in all subjects will be evaluated continually and fully integrated into all DLRMs and considered in all enrollment and dosing decisions. During dose expansion, Amgen will conduct evaluations of the ongoing grade 4 or higher treatment-related adverse event rate to assess if the threshold for possible early trial termination has been reached. If this threshold is met, enrollment to dose expansion will be halted pending review of safety data by the DLRT. After receiving the DLRT recommendation, Amgen will choose to take one of the following actions.

- 1) Terminate the trial

- 2) Amend the protocol to potentially improve the benefit/risk for subjects (eg, increase safety monitoring, modify dose/schedule, mandate [REDACTED])
- 3) Continue dose expansion without any changes

The stopping rules use a Bayesian approach proposed by Thall et al, 1995 to terminate the study if the posterior probability that the grade 4 or higher treatment-related adverse event rate is greater than 20% is $> 80\%$. The stopping boundaries assume a prior distribution of Beta (0.40, 1.60) are presented in [Table 9-1](#) and the operating characteristics with pre-specified batch size of 10 new subjects per batch are presented in [Table 9-2](#). The operating characteristics in [Table 9-2](#) provide the probability of stopping the trial early for given hypothetical true rate of grade 4 or higher treatment-related adverse events, whereas the stopping criteria in [Table 9-2](#) are based on situations where the empirical evidence would result in a posterior probability of $\geq 80\%$ that the true grade 4 or higher treatment-related adverse event rate is $\geq 20\%$.

Table 9-1. Stopping Boundary for Dose Expansion With Posterior Probability of 80% and Grade 4 or Higher Treatment-related Adverse Event Limit of 20%

Number of Subjects	Stop Study if Observing These Many Grade 4 or Higher Treatment-related Adverse Events
10	≥ 4
20	≥ 6
30	≥ 9
40	Dose Expansion Complete

Table 9-2. Operating Characteristics With Batch Size of 10 Subjects

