True Grade 4 or Higher Treatment-related Adverse Event Rate	Probability of Early Stopping of Dose Expansion	Average Dose Expansion Sample Size
0.10	2.0%	39.5
0.15	9.1%	37.6
0.20	23.2%	33.9
0.25	42.2%	28.8
0.30	61.6%	23.4

A formal interim analysis of available safety and efficacy data will occur when the first 10 evaluable subjects enrolled have had the opportunity to complete 4 months on study. This interim analysis will estimate MTD, support the determination of RP2D, conduct futility analysis of objective response rate (ORR), and support the evaluation of benefit/risk profile of AMG 160 as a monotherapy.

[figure not shown]
A futility analysis of ORR will be performed using Bayesian predictive probability (Lee and Liu, 2008) when the first 10 evaluable subjects reach month 4. If the predictive probability of observing ORR response > 15% at the end of the study with 50 evaluable subjects is less than 30%, the study may stop early ($pT = 0.25$). Equivalently, if we observe ≥ 1 objective responder in the first 10 subjects, an additional subjects (up to 40) will be enrolled into the expansion cohort. The predictive probability is calculated with a noninformative prior, Jeffreys prior, Beta(0.5, 0.5).

Similarly, futility analyses will also be conducted during the expansion cohort. The stopping boundaries are presented in [Table 9-3](#). The operating characteristics in [Figure 9-1](#) provide the probability of stopping the trial early for given hypothetical true rate of ORR.

Table 9-3. Objective Response Rate Stopping Boundary

Number of Evaluable Subjects Each Month 4	Stop Study if Observed Objective Response Rate (ORR) Response
10	< 1
20	< 2
30	< 3
40	< 4
50	Study Complete

Figure 9-1. The Probability of Stopping The Trial Early

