9.4.1.1.1 Stopping Rules for Treatment With Siltuximab

Amgen will conduct evaluations of the treatment and outcome of the CRS events treated with siltuximab on an ongoing basis to assess if the threshold for pausing siltuximab treatment has been reached as outlined in the table below. If these stopping rules are met, an ad hoc DLRM will be triggered to review safety data and available PK, [REDACTED], and efficacy data. If recommended by DLRT, the use of siltuximab will resume. The stopping rules to trigger an adhoc DLRM to review siltuximab treatment use a Bayesian approach proposed by Thall et al, 1995; an adhoc DLRM will be triggered if the posterior probability that the CRS progression to grade 3 rate is greater than 30% is > 80% or the posterior probability that the CRS progression to grade 4 rate is greater than 10% is > 80%; or observation of any grade 5 CRS after the event has been treated with siltuximab. The stopping boundaries presented below assume a prior distribution of Beta (0.6, 1.4) for progression to grade 3 CRS and a prior distribution of Beta (0.2, 1.8) for progression to grade 4 CRS. The evaluations could occur more

frequently if necessary to address emerging safety concerns. If the triggered adhoc DLRM coincides with the regular DLRM, they may be combined.

Number of subjects treated with siltuximab	Trigger DLRM if severity of any CRS event treated with siltuximab progresses to Grade 5	
	Or this number of subjects with severity of CRS progressed to Grade 3 after being treated with siltuximab	Or this number of subjects with severity of CRS progressed to Grade 4 after being treated with siltuximab
5	≥ 3	≥ 2
10	≥ 5	≥ 3
15	≥ 7	≥ 3
20	≥ 8	≥ 4
25	≥ 10	≥ 5
30	≥ 12	≥ 5
35	≥ 13	≥ 6
40	≥ 15	≥ 6

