
Recording Adverse Events and Serious Adverse Events

Adverse Event and Serious Adverse Event Recording

- When an adverse event or serious adverse event occurs, it is the responsibility of the investigator to review all documentation (eg, hospital progress notes, laboratory, and diagnostics reports) related to the event.
- The investigator will then record all relevant adverse event/serious adverse event information in the Event case report form (CRF).
- The investigator must assign the following adverse event attributes:
 - Adverse event diagnosis or syndrome(s), if known (if not known, signs or symptoms);
 - Dates of onset and resolution (if resolved);
 - **Assessment of seriousness;**
 - Severity (or toxicity defined below);
 - assessment of relatedness to investigational product, other protocol-required therapies, and/or study-mandated procedure including ⁶⁸Gallium (⁶⁸Ga)- prostate-specific membrane antigen (PSMA)-11, and
 - Action taken.
- If the severity of an adverse event changes from the date of onset to the date of resolution, record a single event for each level of severity on the Event CRF.
- It is not acceptable for the investigator to send photocopies of the subject's medical records to Amgen in lieu of completion of the Event CRF page.
- If specifically requested, the investigator may need to provide additional follow-up information, such as discharge summaries, medical records, or extracts from the medical records. In this case, all subject identifiers, with the exception of the subject number, will be blinded on the copies of the medical records before submission to Amgen.

- The investigator will attempt to establish a diagnosis of the event based on signs, symptoms, and/or other clinical information. In such cases, the diagnosis (not the individual signs/symptoms) will be documented as the adverse event/serious adverse event.

Evaluating Adverse Events and Serious Adverse Events

Assessment of Severity

The investigator will make an assessment of severity for each adverse event and serious adverse event reported during the study. The assessment of severity will be based on:

The **Common Terminology Criteria for Adverse Events**, version 5.0 which is available at the following location:

http://ctep.cancer.gov/protocolDevelopment/electronic_applications/ctc.htm.

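### The expansion safety boundary is worded as a count of adverse events, but its 4/6/9 thresholds were derived for subjects

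*Protocol*

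**What the plan says.** Protocol Section 9.4.1.1 and SAP Section 7.1 describe a Bayesian rule to "terminate the study if the posterior probability that the grade 4 or higher treatment-related adverse event rate is greater than 20% is" above 80%, with a Beta(0.40, 1.60) prior and a "pre-specified batch size of 10 new subjects per batch". The boundary table (Protocol Table 9-1, SAP Table 7-1) has the number of subjects in its rows. The threshold column is headed "Stop Study if Observing These Many Grade 4 or Higher Treatment-related Adverse Events" and reads at least 4, 6 and 9 at 10, 20 and 30 subjects. Table 9-2 (SAP Table 7-2) then gives the "Probability of Early Stopping of Dose Expansion" and the average sample size for five assumed true rates.

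Neither document says whether the rate is per subject or per event. SAP Section 5.1.1 defines a treatment-related adverse event at the level of the event.

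The other boundary built by the same method, for siltuximab (Protocol Section 9.4.1.1.1, SAP Section 7.1.1), does name its unit: "Or this number of subjects with severity of CRS progressed to Grade 3 after being treated with siltuximab".

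Reaching the expansion threshold halts enrollment while the dose level review team examines the safety data. The sponsor may then terminate, amend or continue unchanged.

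**The concern.** A Beta prior on a rate, with subjects as the denominator, describes the proportion of subjects who have an event. A threshold expressed in events is a different quantity: one subject can supply several, and the total can exceed the number of subjects. A team that follows the column heading would run a rule that is stricter than the one whose operating characteristics are printed, by an unknown amount. It could halt expansion because of a few subjects with several events each, when the subject-level evidence is well short of the 80% criterion. Two teams reading the same table could also reach different decisions from the same data.

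**Working it through.** **Inputs.** Prior Beta(0.40, 1.60), limit 20%, posterior cut-off 80%, looks at 10, 20 and 30 subjects with completion at 40, and the figures in Tables 9-1 and 9-2 (all Protocol Section 9.4.1.1).

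**1. Reproduce the boundary with one yes/no outcome per subject.** With r affected subjects among n, the posterior is Beta(0.40 + r, 1.60 + n − r). The threshold is the smallest r with Pr(rate > 0.20) > 0.80.

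| n | Posterior at one fewer | Posterior at threshold | Threshold | Table 9-1 |
|---|---|---|---|---|
| 10 | r = 3: 0.720 | r = 4: 0.895 | 4 | ≥ 4 |
| 20 | r = 5: 0.666 | r = 6: 0.826 | 6 | ≥ 6 |
| 30 | r = 8: 0.783 | r = 9: 0.885 | 9 | ≥ 9 |

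All three agree. The model cannot take an unrestricted event count. With 12 events among 10 subjects, for instance, the second parameter would be 1.60 + 10 − 12 = −0.40, which is not a valid Beta distribution.

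**2. Reproduce Table 9-2 with Binomial(10, p) batches.** Let s10, s20 and s30 be the probabilities of first crossing at each look. The average size is 10·s10 + 20·s20 + 30·s30 + 40·(1 − s10 − s20 − s30). At p = 0.20, s10 = 0.1209, s20 = 0.1109 and s30 = 0.0262, so the average is 1.209 + 2.218 + 0.786 + 40 × 0.742 = 33.89 (printed 33.9).

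| True rate | Average size, computed | Printed | Stopping by n = 20 | Printed | Stopping by n = 30 |
|---|---|---|---|---|---|
| 0.10 | 39.47 | 39.5 | 2.00% | 2.0% | 2.05% |
| 0.15 | 37.62 | 37.6 | 9.08% | 9.1% | 9.7% |
| 0.20 | 33.89 | 33.9 | 23.17% | 23.2% | 25.8% |
| 0.25 | 28.77 | 28.8 | 42.17% | 42.2% | 47.7% |
| 0.30 | 23.41 | 23.4 | 61.64% | 61.6% | 69.2% |

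Both printed columns are per-subject binomial results. The stopping-probability column matches only if the look at 30 is left out. That is a separate matter and does not affect the unit.

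**3. Compare the literal reading with the posterior.** At n = 10:

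- One affected subject: Beta(1.40, 10.60), Pr(rate > 0.20) = 16.4%. Four events in that subject meet the literal threshold.
- Two affected subjects: 44.2%. Two events in each meet the literal threshold.
- Four affected subjects: 89.5%, which is where the model places the boundary.

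**4. Illustrate the size.** The documents do not give events per affected subject. Assume that each affected subject has 1 + Poisson(k − 1) qualifying events, with mean k, and apply 4/6/9 to the event total at 10, 20 and 30 subjects.

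| True subject rate | Subjects counted (k = 1) | k = 1.25 | k = 1.5 | k = 2 |
|---|---|---|---|---|
| 0.10 | 2.1% | 10.4% | 20.2% | 38.4% |
| 0.15 | 9.7% | 27.5% | 42.8% | 64.3% |
| 0.20 | 25.8% | 49.6% | 65.5% | 82.7% |

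At a true subject rate of 0.10, the average expansion size falls from 39.5 to 37.4, 35.0 and 30.7 across the same columns.

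**The case against.** The best reply is that subjects were obviously meant. The text rule is a posterior probability on a rate, the rows are subjects, the siltuximab table counts subjects, and the adverse event summaries use subject incidence (Protocol Section 9.4.2.3.2, SAP Section 9.6.2). This is probably right about intent. But none of those places fixes the unit of this boundary, and the table is what will be applied.

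The second reply is that the plan itself limits clustering, and this stands in part:

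- Protocol Appendix 4 asks for the diagnosis, not each sign or symptom, so multi-organ cytokine release syndrome can be one record.
- Section 8.2.5 generally keeps clinically insignificant laboratory abnormalities out of the adverse event data.
- Table 6-3 ends treatment permanently after several types of grade 4 event, including infusion reaction, cytokine release syndrome and neurological events.
- Section 6.2.2.1 separately suspends accrual after one related grade 5 event, or two of the same related, clinically significant grade 4 events. Some literal crossings would come after accrual had already stopped.

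These provisions make several qualifying events in one subject less common, but they do not exclude distinct or recurrent grade 4+ events.

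A reader might infer from Appendix 4, which says to "record a single event for each level of severity on the Event CRF", that one toxicity moving from grade 4 to 3 and back to 4 gives two grade 4 records. The wording does not support that: taken literally, it gives one record at each grade. The point does not rest on it.

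**Conclusion.** Wrong as written. The threshold is stated in events, while the 4/6/9 boundaries and the Table 9-2 results are for subjects. The per-subject basis is inferred because the text never states it, but the exact match of all three boundaries and all five average sample sizes makes the inference firm.

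The size depends on an assumption. At a true subject rate of 10%, the chance of crossing would be about 10% to 38% instead of 2% if affected subjects averaged 1.25 to 2 qualifying events. Treat this as an illustrative upper range, not an expected effect: the average is assumed, and the recording, discontinuation and accrual-suspension rules pull it down.

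Two stronger readings might be inferred, and the documents support neither. The boundary values are not wrong; they are right for subjects. A crossing does not end the trial automatically; it pauses enrollment for a review at which clustering in one subject would be visible and continuation is allowed. The literal count errs toward extra review, not toward missed harm. The cost is an unnecessary halt and operating characteristics that do not describe the written rule.

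**What to change.** In Protocol Table 9-1 and SAP Table 7-1, head the threshold column as the number of *subjects with at least one grade 4 or higher treatment-related adverse event*. In the paragraph above each table, define the rate as the proportion of such subjects. This matches the unit already used for siltuximab. The 4/6/9 thresholds stay, and no new data, redesign or recalculation of the boundary is needed. The cost is a wording change in two places in each document.

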9.4.2.3.2 Adverse Events

Subject incidence of all treatment-emergent adverse events will be tabulated by system organ class and preferred term and grade. Tables of fatal adverse events, serious adverse events, adverse events leading to withdrawal from investigational product or other protocol-required therapies, and significant treatment emergent adverse events will also be provided. A subgroup analysis of safety with CRS outcome and PK will be performed for subjects who were administered siltuximab.

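### The early-stopping probabilities in protocol Table 9-2 and SAP Table 7-2 leave out the 30-subject safety look that the average-sample-size column includes, so they are too low by 2.6 to 7.6 points at true rates of 0.20 to 0.30.

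*Protocol*

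**What the plan says.** Protocol Section 9.4.1.1 defines a safety rule for dose expansion. The rule is met "if the posterior probability that the grade 4 or higher treatment-related adverse event rate is greater than 20% is" above 80%. On the prior, the text reads "The stopping boundaries assume a prior distribution of Beta (0.40, 1.60) are presented in" Table 9-1. That table gives the boundary under the heading "Stop Study if Observing These Many Grade 4 or Higher Treatment-related Adverse Events": at least 4 at 10 subjects, at least 6 at 20 and at least 9 at 30. Expansion is complete at 40.

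The text adds that "the operating characteristics with pre-specified batch size of 10 new subjects per batch are presented in" Table 9-2. That table has two result columns, "Probability of Early Stopping of Dose Expansion" and the average expansion sample size:

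| True rate | Stopping probability | Average sample size |
|---|---|---|
| 0.10 | 2.0% | 39.5 |
| 0.15 | 9.1% | 37.6 |
| 0.20 | 23.2% | 33.9 |
| 0.25 | 42.2% | 28.8 |
| 0.30 | 61.6% | 23.4 |

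If the boundary is crossed, "enrollment to dose expansion will be halted pending review of safety data by the DLRT", the dose level review team. The sponsor may then terminate, amend or continue unchanged. SAP Section 7.1 repeats the rule and both tables with the same figures, as Tables 7-1 and 7-2.

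**The concern.** Both columns of Table 9-2 should follow from the three looks in Table 9-1. The stopping probabilities looked too low for three looks, although the average sample sizes looked right.

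This column is the documents' quantitative statement of how often the expansion safety rule will trigger. Ethics committees, regulators and the review team would use it to judge whether the rule is sensitive enough at rates above the 20% limit, and how often it would trigger when the rate is at the limit. If the 30-subject look is missing, both readings are wrong.

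**Working it through.** **Inputs (protocol Section 9.4.1.1).** Prior Beta(0.40, 1.60); limit 20%; posterior threshold 80%; batches of 10; boundaries 4/10, 6/20 and 9/30; maximum 40 with no stopping look at 40.

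**Step 1: are the boundaries right?** With x events in n subjects the posterior is Beta(0.40 + x, 1.60 + n − x). The probability that the rate exceeds 20% is:

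| n | At the boundary | One fewer |
|---|---|---|
| 10 | 4: 0.895 | 3: 0.720 |
| 20 | 6: 0.826 | 5: 0.666 |
| 30 | 9: 0.885 | 8: 0.783 |

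Each boundary is the smallest count with a posterior probability above 0.80, so Table 9-1 is correct.

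**Step 2: first-crossing probabilities.** Let c₁₀, c₂₀ and c₃₀ be the probabilities of first crossing at 10, 20 and 30. Each batch adds a Binomial(10, p) count to the running total of subjects who have not yet crossed.

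Worked example at p = 0.30:

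- c₁₀ = P(X ≥ 4) = 0.35039. The probabilities of continuing with 0, 1, 2 or 3 events are 0.02825, 0.12106, 0.23347 and 0.26683.
- c₂₀ = 0.02825 × 0.04735 + 0.12106 × 0.15027 + 0.23347 × 0.35039 + 0.26683 × 0.61722 = 0.26603. The multipliers are the chances of at least 6, 5, 4 and 3 events in the next ten.
- The probabilities of continuing past 20 with 0 to 5 events are 0.00080, 0.00684, 0.02785, 0.07160, 0.12477 and 0.15173. Multiplying these by the chances of at least 9, 8, 7, 6, 5 and 4 events in the next ten (0.00014, 0.00159, 0.01059, 0.04735, 0.15027, 0.35039) and summing gives c₃₀ = 0.07561 (from unrounded terms).

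At all five rates:

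| p | c₁₀ | c₂₀ | c₃₀ |
|---|---|---|---|
| 0.10 | 0.01280 | 0.00719 | 0.00052 |
| 0.15 | 0.04997 | 0.04083 | 0.00645 |
| 0.20 | 0.12087 | 0.11086 | 0.02618 |
| 0.25 | 0.22412 | 0.19762 | 0.05553 |
| 0.30 | 0.35039 | 0.26603 | 0.07561 |

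**Step 3: reproduce the printed stopping probabilities.** Two looks give c₁₀ + c₂₀; three looks add c₃₀.

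| p | Printed | Two looks | Three looks | Shortfall (c₃₀), points |
|---|---|---|---|---|
| 0.10 | 2.0% | 2.00% | 2.05% | 0.05 |
| 0.15 | 9.1% | 9.08% | 9.73% | 0.6 |
| 0.20 | 23.2% | 23.17% | 25.79% | 2.6 |
| 0.25 | 42.2% | 42.17% | 47.73% | 5.6 |
| 0.30 | 61.6% | 61.64% | 69.20% | 7.6 |

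The printed column matches two looks at every rate.

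**Step 4: reproduce the printed average sample sizes.** With three looks, average N = 10c₁₀ + 20c₂₀ + 30c₃₀ + 40(1 − c₁₀ − c₂₀ − c₃₀). At p = 0.30 this is 3.50 + 5.32 + 2.27 + 12.32 = 23.41. Without the third look it is 3.50 + 5.32 + 40 × 0.38358 = 24.17.

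| p | Printed | Two looks | Three looks |
|---|---|---|---|
| 0.10 | 39.5 | 39.47 | 39.47 |
| 0.15 | 37.6 | 37.68 | 37.62 |
| 0.20 | 33.9 | 34.16 | 33.89 |
| 0.25 | 28.8 | 29.32 | 28.77 |
| 0.30 | 23.4 | 24.17 | 23.41 |

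The printed column matches three looks at every rate and fails for two looks from 0.15 upward.

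**Step 5: other explanations.** Looks at 20 and 30 only, looks at 10 and 30 only, an added look at 40, and boundaries raised by one at one or more looks were also tried. None reproduces the printed probabilities at all five rates.

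**The case against.** The practical effect is limited. The boundaries are right, the rule triggers more often than printed, and no hypothesis test or error rate depends on the column. At 0.10 and 0.15 the error is trivial. All of this stands, and it makes this a reporting correction, not a safety defect.

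The column is also not the full probability that expansion is interrupted. Protocol Section 6.2.2.1 separately suspends accrual after one treatment-related grade 5 event, or after two of the same clinically significant grade 4 events. Table 9-3 adds futility looks. The text also speaks of evaluating the rate on an ongoing basis, whereas the calculation assumes looks only after each ten subjects. This stands as well: the figures here are probabilities of crossing the Table 9-1 boundary at the tabulated looks and nothing wider. It does not rescue the printed column, which is presented as the operating characteristic of that same boundary.

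The cause is inferred, since neither document shows the code. The match to one decimal at all five rates makes the inference strong. The contradiction between the two columns does not depend on it. A halt at 30 comes before completion at 40, so it counts as early stopping, and neither document says that it is excluded.

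**Conclusion.** The stopping-probability column is wrong as printed in both documents. Under the rule in Table 9-1 it should read 2.1%, 9.7%, 25.8%, 47.7% and 69.2%. The printed values are too low by 0.05, 0.6, 2.6, 5.6 and 7.6 percentage points. At a true rate of 0.30, the chance of reaching 40 subjects without crossing this boundary is 100 − 69.2 = 30.8%, where the table implies 100 − 61.6 = 38.4%. At the 20% limit itself, the rule triggers about one time in four.

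The result assumes independent subjects with a common event rate, looks only at 10, 20 and 30, and one yes/no outcome per subject. Crossing means a halt for review, not termination.

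The last assumption raises a secondary wording point. The boundary heading, "Stop Study if Observing These Many Grade 4 or Higher Treatment-related Adverse Events", counts events, while the beta-binomial model counts subjects. Subject counting is probably intended. The siltuximab table in Section 9.4.1.1.1 counts subjects ("Or this number of subjects with severity of CRS progressed to Grade 3 after being treated with siltuximab"), and Section 9.4.2.3.2 reports by subject ("Subject incidence of all treatment-emergent adverse events will be tabulated by system organ class and preferred term and grade"). Literal event counting could only raise the trigger probability. The documents do not allow the amount to be stated; it is zero if no subject has more than one such event.

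**What to change.** In protocol Table 9-2 and SAP Table 7-2, replace the stopping probabilities with 2.1%, 9.7%, 25.8%, 47.7% and 69.2%. Leave the boundaries and average sample sizes unchanged.

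As a wording correction, change the boundary heading in protocol Table 9-1 and SAP Table 7-1 to the number of subjects with at least one grade 4 or higher treatment-related adverse event.

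The cost is five numbers and one heading in each document, with no change to the rule or its conduct. Because protocol changes go to ethics committees (protocol Section 11.3), the SAP could be corrected now and the protocol at its next amendment.
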